## 6.2 Randomization (Day 1-Baseline)

Participants who have provided written informed consent, completed all screening procedures and assessments, and who meet all of the inclusion and none of the exclusion criteria will be randomized. Randomization should occur as soon as possible following confirmation that all

inclusion and no exclusion criteria have been met and within no more than 36 hours following initiation of screening.

# 6.3 Dosing Period (Day 1 through Day 8)

After provision of informed consent, participants who satisfy all necessary eligibility criteria will receive doses of ANA001 or matching placebo to begin within approximately 36 hours of site screening and as soon as possible following hospital presentation.

# 6.3.1 Day 1 Assessments

Procedures to be performed and information to be collected on Day 1:

- Height and weight for body mass index (BMI). If a participant is unable to be measured for height and weight, stated height and weight is acceptable.
- NEWS2 (Appendix 2), vital signs, severity of the participant's COVID-19 (Appendix 4), and assessment for presence of subjective clinical signs and symptoms of COVID-19 will be assessed and include presence or absence of: fever, cough (productive or non-productive), sore throat, malaise, headache, muscle pain, gastrointestinal symptoms (i.e., nausea, vomiting, or diarrhea), shortness of breath (with or without exertion), and respiratory distress. Day 1 assessments should be done before the first dose of study drug.
- Record SpO2 on room air and need for supplemental nasal cannula oxygen (including flow rate) if applicable. For patients on supplemental oxygen, SpO2 should be recorded with at least 30 continuous minutes of oxygen.
- A complete physical examination, excluding a genitourinary (GU) examination.
- Administration of study drug (ANA001 or matching placebo). Study drug should be taken with a meal (or NG/OG/PEG tube feeding if applicable).
- Serum chemistry (to be collected before initial dosing), including blood urea nitrogen (BUN), creatinine, sodium, potassium, chloride, carbon dioxide, glucose, direct bilirubin, total bilirubin, alkaline phosphatase (ALP), aspartate aminotransferase (AST), alanine aminotransferase (ALT).
- Hematology and coagulation tests (to be collected before initial dosing) including a complete blood count (CBC), which consists of hemoglobin, hematocrit, total WBC count with a 5-part differential, platelet count, plus a partial thromboplastin time (aPTT), prothrombin time (PT), and an international normalized ratio (INR).
- D-dimer, CRP, cardiac troponin, LDH, and ferritin samples collected for central laboratory testing (to be collected before initial dosing).
- NP swab for confirmation of SARS-CoV-2 with RT-PCR (local site laboratory) per site SOC (to be collected before initial dosing) if part of standard-of-care.
- NP swab for confirmation of SARS-CoV-2 with RT-PCR (central laboratory) (to be collected before initial dosing).
- PK sample collection: Study Part 1 Only: See Appendix 6 for PK sample collection schedule. Refer to the Central Laboratory Manual for additional sample collection and processing instructions. PK samples should be collected in relation to the morning dose of study drug administration.
- WHO Ordinal Scale for Clinical Improvement score (Appendix 1) assessment should be collected/recorded daily and any time the WHO Ordinal Scale for Clinical Improvement score changes. The WHO Ordinal Scale for Clinical Improvement should be recorded with the corresponding date and time of assessment (if unchanged) or with the date and time reflecting the numerical change in the score (if changed).

- Chest X-ray per local standard-of-care.
- AE assessment.
- All systemic concomitant medications (Section 7.4).
- Sequential Organ Failure Assessment (SOFA) score (to be performed at baseline for all participants; Appendix 3).
- Blood for exploratory tests (e.g., IL-6, tissue factor, MCP-1 and IP-10). Blood sample is to be collected before initial dosing.

#### 6.3.2 Daily Assessments (Day 2 through Day 8)

It may not be possible to conduct all study visits in-person due to quarantine and other infection control measures. In case where in-person visits are not possible, telemedicine appointments should be conducted. If the participant is discharged home with study drug for self-administration, visits appropriate for the telemedicine platform are Days 2, 3, 5, 6, 7, and the EOS/Day 60 visit.

For telemedicine appointments, all data should be collected, and the following should be reviewed/discussed in detail with the participant: AEs, concomitant medication, clinical status, and hospital re-admission. Due to the blood and NP swab collection requirements for central laboratory testing on Days 4, 8, 15, and 28, these visits should be conducted in person, either at the stie or with a home visit. If neither is possible, then a telemedicine appointment combined with a home nursing appointment for blood and NP sample collection could be arranged.

Procedures to be performed and information to be collected on Day 2 through Day 8 include:

- NEWS2 (Appendix 2), vital signs, severity of the participant's COVID-19 (Appendix 4), and assessment for presence of subjective clinical signs and symptoms of COVID-19 will be assessed daily and include presence or absence of: fever, cough (productive or non-productive), sore throat, malaise, headache, muscle pain, gastrointestinal symptoms (i.e., nausea, vomiting, or diarrhea), shortness of breath (with or without exertion), and respiratory distress. This should be performed between 2-6 hours after first dose of the day with study drug. Assessments should be collected daily while hospitalized including any day after Day 8 that the participant remains in the hospital.
- Record daily SpO2 on room air and need for supplemental nasal cannula oxygen (including flow rate) if applicable. For patients on supplemental oxygen, SpO2 should be recorded with at least 30 continuous minutes oxygen. Also record any noninvasive ventilation (i.e., No/Yes; if yes designate type). For intubated patients record PaO2 and FiO2 values of the worst P-F ratio of the calendar day. Assessments should be collected daily while hospitalized including any day after Day 8 that the participant remains in the hospital.
- Daily administration of study drug (ANA001 or matching placebo). Study drug should be taken with a meal (or NG/OG/PEG tube feeding if applicable). Total duration of study drug administration is a 7-day course of treatment (i.e., 14 scheduled doses comprised of 56 capsules in total). Participants may be discharged before completing 14 doses and are to be given dosing instructions, the remainder of their therapy, and a diary to record all study drug doses taken.
- Daily serum chemistry (pre-dose), including blood urea nitrogen (BUN), creatinine, sodium, potassium, chloride, carbon dioxide, glucose, direct bilirubin, total bilirubin, alkaline phosphatase (ALP), aspartate aminotransferase (AST), alanine aminotransferase (ALT).

- Daily hematology and coagulation tests (pre-dose) including a complete blood count (CBC), which consists of hematocrit, hemoglobin, total WBC count with a 5-part differential, platelet count, plus a partial thromboplastin time (aPTT), prothrombin time (PT), and an international normalized ratio (INR).
- D-dimer, CRP, and ferritin (to be collected pre-dose on Day 4 and Day 8 only) for central laboratory testing. Cardiac troponin and LDH (to be collected Day 8 or EOT) for central laboratory testing.
- NP swab for confirmation of SARS-CoV-2 with RT-PCR (local site laboratory) per site SOC if part of standard-of-care.
- NP swab for SARS-CoV-2 testing with RT-PCR (to be collected on Day 4 and 8) for central laboratory testing.
- PK sample collection: Study Part 1 Only: See Appendix 6 for PK sample collection schedule. Refer to the Central Laboratory Manual for additional sample collection and processing instructions (Day 1, 2, 3 or Day 4). PK samples should be collected in relation to the morning dose of study drug.
- Daily WHO Ordinal Scale for Clinical Improvement score (Appendix 1) assessment should be collected/recorded daily and any time the WHO Ordinal Scale for Clinical Improvement score changes. The WHO Ordinal Scale for Clinical Improvement should be recorded with the corresponding date and time of assessment (if unchanged) or with the date and time reflecting the numerical change in the score (if changed).
- Chest X-ray per local standard-of-care.
- Daily AE assessment.
- All systemic concomitant medications (Section 7.4).
- SOFA score (to be performed daily only for participants who are admitted in the ICU; Appendix 3).
- Blood for exploratory tests (e.g., IL-6, tissue factor, MCP-1 and IP-10) on Day 8.

#### 6.4 Day 15 (±3 days), and Day 28 (+2 days) Assessments

Procedures to be performed and information to be collected on Day 15 and Day 28:

- NEWS2 (Appendix 2), severity of the participant's COVID-19 (Appendix 4), and assessment for presence of subjective clinical signs and symptoms of COVID-19 including presence or absence of: fever, cough (productive or non-productive), sore throat, malaise, headache, muscle pain, gastrointestinal symptoms (i.e., nausea, vomiting, or diarrhea), shortness of breath (with or without exertion), and respiratory distress. Assessments should be collected daily while hospitalized including any day after Day 8 that the participant remains in the hospital.
- Record SpO2 on room air and need for supplemental nasal cannula oxygen (including flow rate) if applicable. For patients on supplemental oxygen, SpO2 should be recorded with at least 30 continuous minutes of oxygen Also record any noninvasive ventilation (i.e., No/Yes; if yes designate type). For intubated patients record PaO2 and FiO2 values of the worst P-F ratio of the calendar day.
- NP swab confirmation of SARS-CoV-2 with RT-PCR (local site laboratory) per site SOC.
- NP swab for confirmation of SARS-CoV-2 with RT-PCR on Day 15 (±3 days), and Day 28 (+2 days) for central laboratory testing.
- WHO Ordinal Scale for Clinical Improvement score (Appendix 1) assessment should be collected/recorded daily and any time the WHO Ordinal Scale for Clinical Improvement score changes. The WHO Ordinal Scale for Clinical Improvement should

be recorded with the corresponding date and time of assessment (if unchanged) or with the date and time reflecting the numerical change in the score (if changed).

- Chest X-ray per local standard-of-care.
- AE assessment.
- All systemic concomitant medications (Section 7.4).
- SOFA score (to be performed only for participants who are admitted in the ICU; Appendix 3).

#### 6.5 Day 60 (+2 days)/End of Study (EOS)Assessments

Procedures to be performed and information to be collected on Day60/EOS include:

- NEWS2 (Appendix 2), vital signs, severity of the participant's COVID-19 (Appendix 4), and assessment for presence of subjective clinical signs and symptoms of COVID-19 including presence or absence of: fever, cough (productive or non-productive), sore throat, malaise, headache, muscle pain, gastrointestinal symptoms (i.e., nausea, vomiting, or diarrhea), shortness of breath (with or without exertion), and respiratory distress. Assessments should be collected daily while hospitalized including any day after Day 8 that the participant remains in the hospital.
- Record SpO2 on room air and need for supplemental nasal cannula oxygen (including flow rate) if applicable. For patients on supplemental oxygen, SpO2 should be recorded with at least 30 continuous minutes of oxygen Also record any noninvasive ventilation (i.e., No/Yes; if yes designate type). For intubated patients record PaO2 and FiO2 values of the worst P-F ratio of the calendar day.
- NP swab confirmation of SARS-CoV-2 with RT-PCR (local site laboratory) per site SOC.
- NP swab for confirmation of SARS-CoV-2 with RT-PCR for central laboratory testing.
- WHO Ordinal Scale for Clinical Improvement score (Appendix 1) assessment should be collected/recorded daily and any time the WHO Ordinal Scale for Clinical Improvement score changes. The WHO Ordinal Scale for Clinical Improvement should be recorded with the corresponding date and time of assessment (if unchanged) or with the date and time reflecting the numerical change in the score (if changed).
- Chest X-ray per local standard-of-care.
- AE assessment.
- SOFA score (to be performed only for participants who are admitted in the ICU; Appendix 3).

#### 6.6 Discontinuation or Withdrawal

#### 6.6.1 Individual Participants

#### 6.6.1.1 Withdrawal from Study and Lost to Follow-up

An individual participant may withdraw from the study at any time at his/her own request (withdrawal of consent) or may be withdrawn at any time for the following reasons:

• At the request of the primary care provider if he/she thinks the study is no longer in the best interest of the participant.

- The participant is judged by the Investigator or Sponsor to be at significant risk of failing to comply with the provisions of the protocol so as to cause harm to self or seriously interfere with the validity of the study results.
- At the discretion of the Institutional Review Board (IRB)/ Ethics Committee (EC)/ or government agencies as part of their duties.

If the participant withdraws consent for disclosure of future information, the Sponsor may retain and continue to use any data/samples collected before such withdrawal of consent.

At the time of withdrawal from study all procedures scheduled for that study day plus additional assessments (not already planned for that study day) which are scheduled for the end of study drug administration (Study Day 8) or the End of Study (EOS/Day 60) visit should be completed if possible AND if the participant is agreeable. See SOE (Table 1) for data to be collected at the time of withdrawal from study.

A participant will be considered lost to follow-up if unable to be contacted by the study site. The following actions must be taken if a participant fails to present for a study required assessment:

- The site must attempt to contact the participant as soon as possible and counsel the participant on the importance of maintaining the assigned procedure schedule and ascertain whether or not the participant wishes to and/or should continue in the study.
- Before a participant is deemed lost to follow-up, the Investigator or designee must make every effort to regain contact with the participant (where possible, 3 telephone calls and, if necessary and practical, a certified letter to the participant's last known mailing address or local equivalent methods). These contact attempts should be documented in the participant's medical record.
- Should the participant continue to be unreachable, he/she will be considered to have withdrawn from the study with a primary reason of lost to follow-up.

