#### 6.6.1.2 Discontinuation of Study Drug

Participants may be prematurely discontinued from study drug prior to completing a full 7 consecutive days of study drug (i.e., 14 doses administered BID) for any of the following reasons:

- Withdrawal from study or Lost to follow-up (due to reasons listed in Section 6.6.1.1)
- Participant decision (i.e., to be used as reason if participant desires to stop study drug but not withdrawal consent of the study). A participant is free to discontinue study drug therapy at any time without prejudice to further treatment. The Investigator must verify on the eCRF that the participant decision was not based on an adverse event (AE). In such cases, the reason must be recorded as premature discontinuation from study drug due to an AE.
- AE (e.g., continuation of study drug poses a risk to the participant as judged by the Investigator)
- Positive pregnancy test at any time during study drug treatment, OR
- Early discontinuation/termination of the study by Sponsor

In the event that a participant prematurely discontinues study drug, all study procedures and assessments should continue to be performed and collected until the participant completes the EOS/Day 60 visit to the extent possible.

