#### 7.2.3 Extent and Maintenance of Blinding

Both Study Part 1 and Study Part 2 will be blinded. The containers of study drug product allocated to each participant will not identify treatment allocation. Treating Investigators will be blinded. The DMC statistician and the DMC itself will be unblinded for analysis purposes as described in the DMC charter. The Sponsor may also be unblinded at any time if the Sponsor deems this necessary to adequately evaluate potential safety issues. The Sponsor may also be unblinded in accordance with procedures outlined in the statistical analysis plan (SAP).

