#### 9.2 Analysis Populations

The following populations will be considered for analysis of various endpoints:

Randomized Set: It includes all randomized subjects who satisfied the inclusion and exclusion criteria described in this protocol

Full Analysis (or Intent-to-Treat [ITT]) Set: It is the analysis population for the primary efficacy analysis. It includes all randomized subjects classified according to the treatment arm into which they were randomized regardless of the actual treatment received.

Per Protocol Set: It includes all subjects in the Full Analysis (or ITT) Set who satisfy COVID-19 disease criteria at baseline without any major protocol deviations which may affect the evaluation of the primary efficacy endpoints

Safety Set: It includes all randomized subjects, classified according to the actual treatment received regardless of randomization assignment, who received any amount of study drug and have at least one post-baseline safety evaluation. This is the analysis population for all planned safety analyses.

Pharmacokinetic (PK)-Evaluable Set: It consists of all randomized subjects, classified according to the actual treatment received regardless of randomization assignment, who receive at least one dose of study drug. A baseline and at least one pharmacokinetic blood sample following a dose of study treatment is required for inclusion in this analysis set. This is the analysis population for all planned pharmacokinetic analyses.

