7.4. Efficacy Analysis for Secondary Endpoint

The secondary efficacy endpoint for Part 1 of this study is the median time (in hours) from randomization to hospital discharge (where discharge is defined as a score of 1 or 2 in the WHO Ordinal Scale for Clinical Improvement).

Kaplan-Meier curves will be constructed to display time-to- hospital discharge. Participants who are lost to follow-up or ended study early prior to achieving clinical improvement will be censored at the day of the last obtained assessment of their WHO Ordinal Scale for Clinical Improvement. Participants who complete follow-up without hospital discharge will be censored at the day of their Day 60 visit. Participants who die for any reason during the study will be right-censored at Day 60 or date of death, whichever is earlier. For the analysis of this efficacy endpoint, missing scores of the WHO Ordinal Scale for Clinical Improvement will be assumed to be > 2 (*i.e.*, no hospital discharge). Median time-to-clinical improvement and corresponding 95% confidence interval will be estimated from the Kaplan-Meier curves and tabulated for each treatment group.

The Cox proportional hazard method will be used to calculate the hospital discharge rate ratio of ANA001 relative to placebo while controlling for the stratification factors, baseline WHO Ordinal Scale for Clinical Improvement, and number of co-existing conditions. Hospital discharge rate ratio is akin to a hazard ratio but for the beneficial outcome of hospital discharge.

A hospital discharge rate ratio > 1 indicates a benefit for ANA001. Treatment groups will be compared using a stratified log-rank test.

The above analyses will be produced for all participants in the Full Analysis Set and by baseline WHO Ordinal Scale for Clinical Improvement scores. Additionally, the same analysis will be produced for participants in the Per-Protocol Analysis Set and Safety Analysis Set.

If WHO Ordinal Scale are missing at baseline, 6 hours window after first dose will be added for baseline values.

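### When someone other than the participant ends study participation before discharge, no later collection of discharge or vital status is specified, although discharge is on the hospital record

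*Protocol*

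**What the plan says.** Protocol 6.6.1.1 deals with leaving the study. Apart from the participant's own withdrawal of consent, it lists grounds on which others may end participation:

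- Investigator or Sponsor: "The participant is judged by the Investigator or Sponsor to be at significant risk of failing to comply with the provisions of the protocol". A limiting clause follows: "so as to cause harm to self or seriously interfere with the validity of the study results".
- Primary care provider: "At the request of the primary care provider if he/she thinks the study is no longer in the best interest of the participant". Compliance is not mentioned here.
- An ethics committee or government agency acting within its duties.

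At withdrawal, that day's procedures plus the Day 8 or Day 60 assessments are asked for once; the "visit should be completed if possible AND if the participant is agreeable". Neither document provides for collecting discharge or survival afterwards.

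Protocol 6.6.1.2 deals with stopping study drug. It names study withdrawal under 6.6.1.1 as one reason. For anyone who stops drug early it then says, as far as this can be done, that "all study procedures and assessments should continue to be performed and collected until the participant completes the EOS/Day 60 visit".

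On the ITT set, Protocol 9.2 says: "It includes all randomized subjects classified according to the treatment arm into which they were randomized regardless of the actual treatment received". Protocol 6.6.1.3 rules out replacement.

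SAP 7.4 gives one rule for loss to follow-up and for early exit: anyone who "ended study early prior to achieving clinical improvement will be censored at the day of the last obtained assessment", meaning the last WHO scale score. SAP section 1 limits that document to Part 1, where discharge is a secondary endpoint. For Part 2, Protocol 9.3.4 makes time to discharge the primary efficacy endpoint without a censoring rule, and 9.6 plans multiple imputation with details left to the SAP.

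**The concern.** For an inpatient, the date and time of leaving hospital are in the hospital's own records. Obtaining them requires neither capsule-taking nor visit attendance, and Protocol 11.2.1 already has monitors checking endpoints against hospital charts. Ending data collection because someone else ended participation therefore discards an outcome that could be retrieved for a randomized person who belongs in the ITT set.

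Two things are at stake. The first is information: the Part 2 sample size leaves almost no room for lost recoveries. The second is bias: Kaplan-Meier and Cox estimates assume that censored participants would have gone on like those still followed. If such withdrawals were more frequent in one arm and fell mainly on slow recoverers, that arm's discharge rate would be overstated.

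**Working it through.** **1. The passages side by side**

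- Stops drug but stays in the study: followed to Day 60 (Protocol 6.6.1.2).
- Withdrawn by others after discharge: the discharge time is already recorded and is kept.
- Withdrawn by others before discharge: one exit set (6.6.1.1), then nothing specified. Part 1 censors at the last WHO score; Part 2 has no stated rule.
- Because 6.6.1.2 counts study withdrawal as a reason for stopping drug, its Day 60 sentence literally covers these people too. 6.6.1.1 reads as if collection ends with the exit set. The two must be reconciled.

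**2. The plan's own figure (Protocol 9.1.2)**

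Inputs: medians 15 and 11 days, two-sided 0.05, 85% power, 1:1 allocation. With exponential times the rate ratio is 15/11 = 1.364.

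Schoenfeld events = 4(1.960 + 1.036)² / (ln 1.364)² = 374. This matches the plan.

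With uniform accrual over 180 days and at least 30 days of follow-up, the event probabilities are 0.970 (placebo) and 0.987 (ANA001), mean 0.978. The number needed is 374/0.978 = 383, against the stated 376 (1.9% apart). No dropout term is stated, and none is needed to come near 376. The plan needs 374/376 = 99.5% of participants to recover under observation.

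**3. Information lost**

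Power = Φ(½√events × ln(15/11) − 1.96). The documents give no loss rate, so the fractions are assumed:

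- none lost: 374 events, 85.1%
- 5% lost: 355.3 events, 83.2%
- 10% lost: 336.6 events, 81.2%

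**4. Bias in a worst case**

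Assume no drug effect, exponential stays with median 15 days in both arms, and follow-up to Day 60. A fraction f of the ANA001 arm only, all with a true stay over 15 days, is withdrawn on Days 2 to 7 (mean 4.5) and censored.

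- Rate λ = ln 2/15 = 0.04621 per day.
- Without withdrawal: events per person 1 − 2⁻⁴ = 0.9375; days at risk 0.9375/λ = 20.29.
- Each withdrawn person would have contributed 1 − 2⁻³ = 0.875 events and 15 + 0.875/λ = 33.94 days, but contributes 0 events and 4.5 days.
- f = 5%: (0.9375 − 0.04375)/(20.29 − 1.47) = 0.0475; divided by λ this gives 1.03.
- f = 10%: (0.9375 − 0.0875)/(20.29 − 2.94) = 0.0490; divided by λ this gives 1.06.

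**5. Simulation, and relaxing the assumptions**

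The setting is as in step 4, with 188 per arm. Rejection is one-sided in favour of ANA001 at z > 1.96. The first five rows use 20,000 trials each and the last two 10,000 (Monte Carlo error 0.1 to 0.2 points).

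| Withdrawn, ANA001 / placebo | Drawn from | Rate ratio | Rejection |
|---|---|---|---|
| 0 / 0 | none | 1.00 | 2.7% |
| 9 / 0 | stay > 15 days | 1.03 | 4.5% |
| 19 / 0 | stay > 15 days | 1.06 | 8.4% |
| 19 / 9 | stay > 15 days | 1.04 | 5.4% |
| 9 / 9 | stay > 15 days | 1.00 | 2.7% |
| 9 / 4 | stay > 15 days | 1.02 | 3.6% |
| 9 / 0 | stay > 7 days | 1.01 | 2.9% |

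On the protocol's two-sided 0.05 test, 9 / 0 slow recoverers gives 6.2%, against 5.1% with none withdrawn.

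**The case against.** The strongest reply is that the plan already keeps the people one would worry about.

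- Refusing capsules, for nausea or any other reason, falls under participant decision or adverse event in Protocol 6.6.1.2. Both stop drug only, with follow-up to Day 60. Protocol 4.1 also asks for the remaining assessments in those who cannot finish the course.
- Protocol 7.4.2 keeps patients who deteriorate in the study.
- The compliance ground carries a high threshold, so ordinary missed doses do not meet it.
- The explicit censoring rule belongs to Part 1, for which Protocol 9.3 plans no formal inference. Part 2 points to multiple imputation.

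All of this stands. It means that such withdrawals should be few and that a link with tolerability or prognosis is possible rather than shown. It does not supply the missing outcome for those who are withdrawn. Imputing a discharge time that the chart holds is a poorer choice than reading it, and SAP 7.4's assumption that a missing score means no discharge does not recover it either.

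A reader might go further in three ways that the documents do not support:

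- That a primary care provider may remove someone for expected non-compliance. That ground is best interest only.
- That a sponsor who knows the allocation could remove participants selectively. Protocol 7.2.3 says "The Sponsor may also be unblinded at any time if the Sponsor deems this necessary to adequately evaluate potential safety issues", and otherwise refers to SAP procedures. Nothing links unblinding to withdrawal decisions.
- That the false-positive rate is inflated to some 8%. That figure needs 10% loss in one arm only, all of it slow recoverers.

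**Conclusion.** The point holds as a gap in outcome collection. Participants withdrawn by others before discharge have no specified later collection of discharge or vital status. Protocol 6.6.1.1 and 6.6.1.2 do not agree on whether follow-up continues. Part 1 censors these participants, and Part 2 has no written rule for its primary efficacy endpoint.

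The size cannot be fixed from the documents, since they give no withdrawal rate. The ratio of 1.03 to 1.06 is a ceiling for the assumed 5% to 10% loss. It rests on one-arm loss, slow recoverers only, exponential stays and no drug effect, and it disappears with balanced loss. Losing 5% to 10% of the required recoveries would cost about 2 to 4 points of power. It would be too strong to say that the ITT principle is undone: the analysis set keeps everyone, and what may be missing is the outcome of a few. The improvement is worth making because it is cheap.

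**What to change.** - In Protocol 6.6.1.1, state that withdrawal by anyone other than the participant does not end outcome collection, and align 6.6.1.2 with this.
- Unless the participant refuses use of records, collect discharge date and time and vital status to Day 60 from the hospital chart. 6.6.1.1 already treats withdrawal of consent for disclosure of future information as a case of its own, so the distinction is available.
- In SAP 7.4, use the retrieved discharge instead of censoring at the last WHO score. Censor at the last score only where nothing can be retrieved.
- Write the same rule for Part 2, and reserve the multiple imputation of Protocol 9.6 for outcomes that remain missing.
- Report by arm how many participants were withdrawn by others before discharge, and how many outcomes were retrieved.

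Who may stop study drug, and on what grounds, should stay as it is; so should the listed grounds for withdrawal. The statistical problem needs only the outcome data.

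The cost is wording in the protocol, SAP and consent form, and a chart look-up for a few participants. No visits are added.
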